8.3.3. Additional Within-VFCC-Arm-Testing and Within-Collagenase-Control-Arm-Testing

The appropriate generalized linear modeling will be used to analyze the primary or secondary endpoint (percent change in wound area considered clean/viable/healthy, total wound area, and wound volume) with the following potential fixed effects: clinical site; baseline total wound area; body mass index; treatment arm; and indicator of baseline wound undermining.

The within-arm testing will be based on the least square means estimate for the VFCC or Collagenase treatment arm derived from the final model used for the between-treatment testing in the primary or secondary analyses. This exploratory testing will occur in conjunction with the within-VFCC-treatment arm testing described previously in section 8.2.4. This testing plan will examine within-VFCC and within-collagenase changes in percent wound surface area assessed as clean, healthy and viable; percent total wound area, and percent wound volume at all study visits relative to baseline. These analyses will be carried out for the mITT and FAS (with NOCB/LOCF imputation).

8.3.4. Absolute change in wound area (cm²) considered clean/healthy/viable relative to baseline

The absolute change from baseline to Day X upon the final dressing removal in the wound bed surface area (cm²) considered to be clean, healthy, and viable

This exploratory endpoint is defined as the absolute difference in the wound bed surface area (cm²) considered to be clean, healthy, and viable between the Day X assessment value and baseline value. The absolute value of clean, healthy, and viable tissue in the wound bed surface area (absCHV) is defined as the percent of clean, healthy, and viable tissue (pctCHV) (defined in section 8.4) divided by 100 and multiplied by total wound area.

The absolute change from baseline to Day X upon the final dressing removal in the wound bed surface area (cm²) considered to be clean, healthy, and viable is then defined as:

$$\Delta absCHV = absCHVX - absCHV0$$

where,

absCHV0 = absolute value of clean, healthy and viable tissue in the wound bed surface area (cm²) at baseline

absCHVX = absolute value of clean, healthy and viable tissue in the wound bed surface area (cm²) at Day X (e.g. Day 6-9) upon final dressing removal

The following hypothesis will be tested:

Null: $\Delta absCHV_{VFCC} - \Delta absCHV_{Control} = 0$
 $\neq 0$

Alternative: $\Delta absCHV_{VFCC} - \Delta absCHV_{Control}$

where $\Delta absCHV_{VFCC} - \Delta absCHV_{Control}$ is the difference in the absolute value change in the wound bed surface area (cm²) considered to be clean, healthy, and viable from baseline to Day X upon the final dressing removal between the VFCC with NPWTi-d group and Control group.

The appropriate generalized linear modeling will be used to analyze the endpoint with potential fixed effects: clinical site; baseline total wound area; body mass index [BMI]; treatment arm and indicator of baseline wound undermining. If any of the covariates (except treatment arm and site ID) is not statistically significant at the 0.1 level, then the non-significant term(s) will be removed from the model and the updated model will be re-run. These endpoints will be summarized based on the mITT and FAS (with NOCB/LOCF imputation) analysis sets.

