### **8.3.4. Analysis of Primary Endpoint**

The primary endpoint will be calculated per the definition in Section 8.1.1. Based on the mITT analysis set, the primary endpoint will be summarized by treatment group and overall.

The null and alternative hypotheses for the primary endpoint are:

Null:  $\Delta_{VFCC - Control} = 0$       Alternative:  $\Delta_{VFCC - Control} \neq 0$

where  $\Delta_{VFCC - Control}$  is the difference in the percent change in the wound bed surface area ( $\text{cm}^2$ ) considered to be clean, healthy, and viable between the VFCC and NPWTi-d group and Control group.

Assessments will be taken at multiple visits for each Subject during the study. The primary endpoint will be analyzed using a repeated measures analysis of covariance model (ANCOVA) with treatment arm, visit, wound undermining measurement, clinical site, and treatment by visit (Note: if clinical site or treatment by visit are not statistically significant, then the non-significant term(s) will be removed from the model and the updated model will be re-run). The analysis will be based on the mITT analysis set.

If appropriate, supportive/exploratory analyses of the primary endpoint may include:

- repeat the analysis above on the ITT and Per-Protocol analysis sets
- a two-sample t-test or a Wilcoxon Rank-Sum test without adjusting for wound undermining
- analyses comparing the treatment groups considering covariates (eg, age, body mass index [BMI], race/ethnicity, sex, wound undermining, and co-morbidities) and subsets of the data

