4.1.3. Exploratory Endpoint(s)

The exploratory endpoints for this study include:

- Repeated measures of the change in percent of clean, healthy, viable tissue (%) over time, analyzing the rate of change and differences at study visits.
- Repeated measures of the percent change in total wound volume (%) over time, analyzing the rate of change and differences at study visits.
- Repeated measures of the percent change in total wound area (%) over time, analyzing the rate of change and differences at study visits.
- The absolute change from baseline to Day 6-9 upon the final dressing removal in the wound bed surface area (cm^2) considered to be clean, healthy, and viable.
- The absolute change from baseline to Day 6-9 in the total wound area (cm^2).
- The absolute change from baseline to Day 6-9 in the total wound volume (cm^3).
- Repeated measures of the absolute change in total wound volume, total wound area and viable wound area over time, analyzing the rate of change and differences at study visits.
- The percent change and absolute change of granulation tissue from baseline to Day 6-9 upon the final dressing removal
- Number of treatment applications and/or dressing changes per Subject (i.e., collagenase ointment applications versus VFCC applications); analyzed by treatment duration, wound size, and/or wound type, as appropriate.
- Total time to perform treatment applications and/or dressing changes per Subject; analyzed by wound size and/or wound type, as appropriate.
- Within-VFCC-treatment changes in the percent of wound bed surface area considered clean, healthy, viable tissue (%) at Day 2-3 and Day 4-6 study visits relative to baseline.
- Within-VFCC-treatment changes in the percent of total wound area (%) at Day 2-3 and Day 4-6 study visits relative to baseline.
- Within-VFCC-treatment changes in the percent of wound volume (%) at Day 2-3 and Day 4-6 study visits relative to baseline.

- Within-Collagenase-control-treatment changes in the percent wound surface area considered clean, healthy and viable; changes in percent wound area; and changes in percent wound volume at all study visits relative to baseline.

In addition to these exploratory endpoints, the following data will be collected from Subjects in one of the groups:

- Total number of collagenase ointment tubes used per Subject; analyzed by treatment duration, wound size, and/or wound type, as appropriate.

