8. EFFICACY ANALYSIS

8.1. Primary Efficacy Analysis

The primary endpoint is the change in the percent of wound bed surface area (cm^2) considered to be clean, healthy, and viable from baseline to Day 6-9 upon the final dressing removal. The percentage of clean, healthy, and viable tissue (pctCHV) is defined as the sum of percentages of viable Bone/Cartilage/Ligament/Tissue (B/C/L/T), viable fat, viable muscle/fascia, and granulation tissue. The change in percent (ΔpctCHV) of clean, healthy, and viable tissue from baseline to Day 6-9 upon the final dressing removal is defined as:

$$\Delta\text{pctCHV} = \text{pctCHV}_4 - \text{pctCHV}_0$$

where,

pctCHV₀ = percent of clean, healthy, and viable tissue at baseline

pctCHV₄ = percent of clean, healthy, and viable tissue at Day 6-9 upon final dressing removal.

The following hypothesis will be tested:

Null: $\Delta\text{pctCHV}_{\text{VFCC}} - \Delta\text{pctCHV}_{\text{Control}} = 0$
 $\neq 0$

Alternative: $\Delta\text{pctCHV}_{\text{VFCC}} - \Delta\text{pctCHV}_{\text{Control}}$

where $\Delta pctCHV_{VFCC} - \Delta pctCHV_{Control}$ is the difference of the change in percent of wound bed surface area (cm^2) considered to be clean, healthy, and viable between the VFCC with NPWTi-d group and the Control group.

Generalized linear modeling will be used to analyze the primary endpoint with the following fixed effects: clinical site; baseline percent of wound bed surface considered clean, healthy and viable [pctCHV0]; body mass index [BMI]; treatment arm and indicator of baseline wound undermining.

If any of the covariates (except treatment arm and site ID) is not statistically significant at the 0.1 level, then the non-significant term(s) will be removed from the model and the updated model will be re-run. The analysis will be conducted at the α -level determined by the O'Brien-Fleming α -spending function² and observed fraction time.

```
proc mixed data=adeff;
  class trtp siteid undermin;
  model chg=bmi base trtp siteid undermin / ddfm=kr cl;
  lsmeans trtp/ diff cl;
run;
```

The analysis will be conducted at a final alpha level as determined by the O'Brien-Fleming α -spending function². The primary analysis will be based on the mITT analysis set, and the test of the difference of the least square means estimates.

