8.2.3. Percent change in total wound volume (cm^3) relative to baseline

The percent change in total wound volume ($\Delta pctVol$) from baseline to Day X upon the final dressing removal is defined as the difference in total wound area between the Day X assessment and baseline assessment, divided by the baseline value and multiplied by 100.

$$\Delta pctVol = \left(\frac{VolX - Vol0}{Vol0} \right) \times 100$$

where,

Vol0 = the total wound volume at baseline

VolX = the total wound volume at Day X (e.g. Day 6-9) upon final dressing removal.

The following hypothesis will be tested:

Null: $\Delta pctVol_{VFCC} - \Delta pctVol_{Control} = 0$
 $\neq 0$

Alternative: $\Delta pctVol_{VFCC} - \Delta pctVol_{Control}$

where $\Delta pctVol_{VFCC} - \Delta pctVol_{Control}$ is the difference of percent change in total wound volume (cm^3) between the VFCC with NPWTi-d group and Control group.

The appropriate generalized linear modeling will be used to analyze the endpoint with potential fixed effects: clinical site; baseline total wound area; body mass index [BMI]; treatment arm and indicator of baseline wound undermining. These analyses will be carried out for the mITT and FAS (with NOCB/LOCF imputation).

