8.2.4. Within-VFCC-Treatment Arm Testing

The appropriate generalized linear modeling will be used to analyze the primary or secondary endpoint (percent change in wound area considered clean/viable/healthy, total wound area, and wound volume) with the following potential fixed effects: clinical site; baseline total wound area; body mass index; treatment arm; and indicator of baseline wound undermining.

The within-arm testing will be based on the least square means estimate for the VFCC treatment arm derived from the final model used for the between-treatment testing in the primary or secondary analyses. These analyses will be carried out for the mITT and FAS (with NOCB/LOCF imputation).

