8.3.2. Repeated Measures Analyses

In addition, a repeated measures analysis of covariance model (ANCOVA) will be applied to analyze the endpoints of percent of wound bed clean/viable/healthy, total wound volume and total wound area. Fixed covariates of clinical site, treatment arm, wound undermining measurement, visit, and treatment by visit. If clinical site or treatment by visit is not statistically significant, then the non-significant term(s) will be removed from the model, and the updated model will be re-run. Covariance structure will be unstructured, AR(1) or TOEFL, selected based on best fit (likelihood ratio tests or based on appropriate fit statistics).

These endpoints will be summarized based on the mITT and the FAS (with NOCB/LOCF imputation) analysis sets.

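### Exploratory models for viable area, volume and granulation leave out the outcome's own baseline, an avoidable loss of precision

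*SAP*

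**What the plan says.** The primary model in SAP 8.1 adjusts for "baseline percent of wound bed surface considered clean, healthy and viable [pctCHV0", which is the starting value of its own outcome. The total-area models (8.2.2 and 8.3.5) adjust for baseline total wound area, again the outcome's own baseline.

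The same list is then used for outcomes to which it does not belong. SAP 8.3.4 (viable area), 8.3.6 (absolute volume), 8.3.7 (percent granulation) and 8.3.8 (granulation area) each offer "potential fixed effects: clinical site; baseline total wound area; body mass index [BMI]; treatment arm and indicator of baseline wound undermining". SAP 8.2.3 (percent change in volume) has this list too. In 8.3.4 to 8.3.8 a selection rule follows: "If any of the covariates (except treatment arm and site ID) is not statistically significant at the 0.1 level", the term is dropped. The rule only removes terms.

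The exploratory repeated-measures model in SAP 8.3.2 has no baseline term at all: "Fixed covariates of clinical site, treatment arm, wound undermining measurement, visit, and treatment by visit". This is the list of the Protocol's primary model (Protocol 8.3.4), which was specified "with treatment arm, visit, wound undermining measurement, clinical site, and treatment by visit". SAP 8.3.2 names its responses as levels, whereas SAP 4.1.3 describes them as changes, for example "Repeated measures of the percent change in total wound volume (%) over time, analyzing the rate of change and differences at study visits".

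SAP 8.3.4 and 8.3.6 are run on the mITT set and on the FAS with NOCB/LOCF imputation. SAP 8.3.7 and 8.3.8 are run on the ITT set without imputation.

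**The concern.** A change score usually correlates with its own starting value: wounds with little viable tissue have more to gain, and deep wounds have more volume to lose. Adjusting for that value removes variance from the treatment comparison. Baseline total area is only a partial substitute. It says little about what share of the bed is viable or granulating, and nothing about depth. SAP 8.1 uses the own baseline, and the SAP gives no reason for treating these outcomes differently.

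At stake is the width of the intervals for exploratory between-arm differences in a trial with about 46 evaluable subjects spread over about 15 sites.

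**Working it through.** **1. Which models contain the own baseline**

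| SAP section | Outcome | Baseline term listed | Own baseline |
|---|---|---|---|
| 8.1 | change in viable percent | pctCHV0 | included |
| 8.2.2, 8.3.5 | change in total area | total area | included |
| 8.3.4 | change in viable area (cm²) | total area | absCHV0 missing |
| 8.3.6 | change in volume | total area | Vol0 missing |
| 8.3.7 | change in percent granulation | total area | Granulation0 missing |
| 8.3.8 | change in granulation area (cm²) | total area | Area0 × Granulation0/100 missing |
| 8.2.3 | percent change in volume | total area | Vol0 missing |

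**2. The plan's own figure.** The documents state no precision for these models, so the only design figure to reproduce is the sample size (Protocol 8.4.1, SAP 6.2). With a difference of 20 and an SD of 22, p = Φ(20/(22√2)) = 0.740. Noether's formula gives N = (1.960 + 0.842)²/(3 × 0.240²) ≈ 45.5, hence 23 per group. With 23% loss, 60 × 0.77 ≈ 46. The figure is reproduced, and 46 subjects and 15 sites are used below.

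**3. Cost of one more term.** The listed model uses 1 (intercept) + 14 (sites) + 4 (arm, BMI, undermining, area) = 19 parameters, which leaves 46 − 19 = 27 residual df. In simulation, a useless extra covariate gives a CI ratio (without/with) of 0.980, so adding it widens the CI by about 2%. For partial correlation r with the outcome, the ratio is about 0.980/√(1 − r²): 1.000 at r = 0.2, 1.027 at 0.3 and 1.132 at 0.5. Break-even is near r = 0.2.

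**4. Gain from the own baseline.** All distributions here are assumptions. Area is lognormal with median 40 cm², log-SD 0.5 or 0.7, and at least 16 cm². Viable percent at baseline is uniform on 0 to 66.7, with gains of 20/40 or 20/20 points, error SD 22, and slope of final on baseline 0.3, 0.5 or 0.8. Granulation at baseline is 0 to 50%, with gains of 15/30 or 15/15 and error SD 18. For volume, log-depth SD is 0.4 or 0.7, log-volume slope 0.8 to 1.1, log error SD 0.2 or 0.35, and direct log-area effect 0, 0.1 or 0.2. There were 400 datasets per scenario. The table gives the CI width without the own baseline divided by the width with it added and area kept.

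| Outcome | Min | Median | Max |
|---|---|---|---|
| Viable area (8.3.4) | 1.009 | 1.118 | 1.235 |
| Granulation area (8.3.8) | 1.002 | 1.091 | 1.180 |
| Percent granulation (8.3.7) | 0.992 | 1.060 | 1.141 |
| Absolute volume (8.3.6), area effect 0 | 1.012 | 1.138 | 2.422 |
| Absolute volume, area effect 0.1 | 1.013 | 1.121 | 2.186 |
| Absolute volume, area effect 0.2 | 1.018 | 1.101 | 1.999 |

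Cross-check: the large-sample residual variance with both terms, relative to area alone, was 0.66 to 0.96 for viable area. Then 0.980/√0.66 = 1.21 and 0.980/√0.96 = 1.00, close to the simulated range. For granulation area, 0.71 to 0.98 gives 1.16 down to 0.99.

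SAP 8.3.7 and 8.3.8 use ITT without imputation, so up to 60 subjects. At n = 60 the medians were about +10% (granulation area) and +7% (percent granulation).

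**5. Why absolute volume is so uncertain.** Suppose baseline and final variances are equal and area acts only through Vol0. Let ρ be the correlation of Vol0 with final volume and r that of area with Vol0. The variance ratio is [2(1 − ρ) − r²(1 − ρ)²]/(1 − ρ²).
- ρ = 0.3, r = 0.5: 1.2775/0.91 = 1.404, SE +18.5%
- ρ = 0.5, r = 0.7: 0.8775/0.75 = 1.170, SE +8.2%
- ρ = 0.9, r = 0.9: 0.1919/0.19 = 1.010, SE +0.5%

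Skewed volumes, or shrinkage that varies with wound size, break the equal-variance assumption and produce the maxima of 2.0 to 2.4.

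**6. Percent change in volume (8.2.3).** Adding Vol0 gives ratios from 0.975 to 1.106, with medians of 0.993 to 0.995. The CI became wider in 22 + 21 + 22 = 65 of 96 scenarios. Dividing by Vol0 has already removed most of the dependence.

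**7. Repeated measures (8.3.2).** With only post-baseline visits modelled and no baseline term, precision is lost for either type of response. For a level, the large-sample SE ratio is 1/√(1 − ρ²): +15% at ρ = 0.5 and +40% at 0.7. For a change with equal variances it is √(2/(1 + ρ)): +15% and +8%. If Day 0 is itself a response visit, the baseline is already in the model and should not be entered again.

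**The case against.** The best case for leaving the text alone is that these endpoints are exploratory with no multiplicity control, that the effects are called potential under appropriate modelling, that every correlation above is assumed, and that the lower bounds reach zero or just below. All of that is true, and it limits the weight of the point. But flexible wording does not help when no own-baseline term is among the candidates and the selection rule only deletes.

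A second objection concerns the FAS. SAP 6.3.1 fills a missing baseline with the next observation, so the added covariate could be a post-treatment value there. This stands as a caution. It already applies to the baseline area term now in 8.3.4 and 8.3.6.

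Three stronger readings are tempting.
- A reader might infer bias. Treatment is randomized, so omitting a baseline covariate does not by itself shift the estimate on average. The mITT requirement of a Day 6-9 assessment is a post-randomization selection, but a separate matter.
- A reader might infer that the secondary volume tests in the Holm family lose power. Step 6 shows a net effect of about nil.
- A reader might want the own baseline exempted from the 0.1-level removal rule. At n = 46, forcing the term in gave no gain over letting the rule act: median ratio 1.131 against 1.133 for viable area, and 1.063 against 1.066 for percent granulation.

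**Conclusion.** The omission in SAP 8.3.4 and 8.3.6 to 8.3.8 is a matter of text and is not in doubt. Its effect is an avoidable loss of precision in exploratory estimates. For viable area and granulation the loss is modest, with medians of about 6 to 12%. For absolute volume the typical loss is similar, but its upper end cannot be fixed without knowing how skewed the volumes are and whether shrinkage depends on wound size. In SAP 8.3.2 the size depends on a response and visit structure that the SAP does not settle.

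The point is minor in consequence. No primary, Holm or sample-size conclusion rests on these models. The sizes hold only under the assumed distributions; the direction is more secure, except for percent granulation, where a weakly predictive baseline could cost about 1%.

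**What to change.** Before database lock, amend the SAP as follows.
- 8.3.4: add absCHV0 and keep baseline total area.
- 8.3.6: add Vol0 and keep baseline total area.
- 8.3.8: add Area0 × Granulation0/100 and keep baseline total area.
- 8.3.7: add Granulation0.
- 8.3.2: state the response and whether Day 0 is a modelled visit. If only post-baseline visits are modelled, whether as change, percent change or level, add the outcome's baseline. If Day 0 is a response visit, do not.

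For the cm² tissue outcomes the own baseline must be added, not swapped in for area: replacement made precision worse (variance ratio, listed model over replacement, 0.82 to 0.90). Where the FAS contains NOCB baselines, take the mITT result as the main reading. SAP 8.2.3 and the 0.1-level rule need no change for this purpose.

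The cost is wording plus one degree of freedom per model, about 2% on the CI if the covariate is useless. The baselines come from the Day 0 3D image (Protocol 4.10 and 4.14). Each change score already needs its baseline, so no further subject is excluded.

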8.3.5. The absolute change in the total wound area (cm²) relative to baseline

This exploratory endpoint is defined as the absolute difference in wound area between the Day X assessment value and baseline value:

$$\Delta absArea = AreaX - Area0$$

where,

Area0 = the total wound area at baseline

AreaX = the total wound area at Day X (e.g. Day 6-9) upon final dressing removal.

The following hypothesis will be tested:

Null: $\Delta absArea_{VFCC} - \Delta absArea_{Control} = 0$
 $\Delta absArea_{Control} \neq 0$

Alternative: $\Delta absArea_{VFCC} -$

where $\Delta absArea_{VFCC} - \Delta absArea_{Control}$ is the absolute difference in the total wound area from baseline to Day X upon final dressing removal between the VFCC with NPWTi-d group and Control group.

The appropriate generalized linear modeling will be used to analyze the endpoint with potential fixed effects: clinical site; baseline total wound area; body mass index [BMI]; treatment arm and indicator of baseline wound undermining. If any of the covariates (except treatment arm and site

ID) is not statistically significant at the 0.1 level, then the non-significant term(s) will be removed from the model and the updated model will be re-run. These endpoints will be summarized based on the mITT and FAS (with NOCB/LOCF imputation) analysis sets.

8.3.6. The absolute change in the total wound volume (cm³) relative to baseline

This exploratory endpoint is defined as the absolute difference in wound volume between the Day X assessment value and baseline value:

$$\Delta absVol = VolX - Vol0$$

where,

Vol0 = the total wound volume at baseline

VolX = the total wound volume at Day X (e.g. Day 6-9) upon final dressing removal.

The following hypothesis will be tested:

Null: $\Delta absVol_{VFCC} - \Delta absVol_{Control} = 0$
 $\neq 0$

Alternative: $\Delta absVol_{VFCC} - \Delta absVol_{Control}$

where $\Delta absVol_{VFCC} - \Delta absVol_{Control}$ is the absolute difference in the total wound volume from baseline to Day X upon final dressing removal between the VFCC with NPWTi-d group and Control group.

The appropriate generalized linear modeling will be used to analyze the endpoint with potential fixed effects: clinical site; baseline total wound area; body mass index [BMI]; treatment arm and indicator of baseline wound undermining. If any of the covariates (except treatment arm and site ID) is not statistically significant at the 0.1 level, then the non-significant term(s) will be removed from the model and the updated model will be re-run. These endpoints will be summarized based on the mITT and FAS (with NOCB/LOCF imputation) analysis sets.

